## 9.4 Duration and Grade of AE Capture

AEs will be captured starting with the initiation of study treatment through 30 days after the last administration of the study treatment.

### 9.4.1 AE Grading

Toxicities will be graded using the NCI Common Terminology Criteria for Adverse Events (CTCAE) Version 4.03. Citing the website under this section in the protocol rather than printing the entire document is sufficient unless the study is modifying the criteria. The scale in its entirety can be found at:

[http://evs.nci.nih.gov/ftp1/CTCAE/CTCAE\\_4.03\\_2010-06-14\\_QuickReference\\_8.5x11.pdf](http://evs.nci.nih.gov/ftp1/CTCAE/CTCAE_4.03_2010-06-14_QuickReference_8.5x11.pdf)

## 10.0 DATA AND SAFETY MONITORING PLAN

The PI of the study will have primary responsibility for ensuring that the protocol is conducted as approved by the FHCRC Scientific Review Committee and Institutional Review Board. The PI will ensure that the monitoring plan is followed, that all data required for oversight of monitoring are accurately reported to the FHCRC/UW Cancer Consortium Data and Safety Monitoring Committee (DSMC), that all adverse events are reported according to the protocol guidelines, and that any adverse reactions reflecting patient safety concerns are appropriately reported. The PI or designee will personally review with the Research Nurse the clinical course of all the enrolled patients weekly. A delegation log of authority will be kept to delineate the role of co-investigators (**Appendix K**).

Under the provisions of the Institutional Data Safety and Monitoring Plan, the Cancer Consortium Clinical Research Support Office provides monitoring for Good Clinical Practice and compliance by qualified monitors unaffiliated with the conduct of the study. Monitoring visits are conducted in accordance with the Cancer Consortium Data and Safety Monitoring Plan.

This protocol will also be monitored by a dedicated DSMB on a semi-annual basis. Enrollment, response and toxicity data will be reviewed. The DSMB has the authority to terminate the study, hold enrollment, or suggest modifications to the protocol as indicated.

An annual review of the progress of the study with respect to the monitoring plan will be performed by the DSMC. The DSMC will review the number of subjects and unanticipated problems. The DSMC will also review DSMB reports regarding accrual, stopping rules, protocol adherence to the data and safety monitoring plan, as well as DSMB recommendations. If the DSMC finds a study to be continuing accrual in violation of the study design or the recommendation of the DSMB, the DSMC has the authority to suspend trial accrual.

## 11.0 STUDY AGENT INFORMATION

### 11.1 Background Investigational drug: Deferasirox

Deferasirox is an orally active chelator that is highly selective for iron (III). It is a tridentate ligand that binds iron with high affinity in a 2:1 ratio. Two molecules of deferasirox form a complete complex with Fe3+.

The high potency of deferasirox in mobilizing tissue iron and promoting iron excretion was demonstrated both in vitro and in vivo model systems. Deferasirox is eliminated from the body by hepatic glucuronidation and biliary excretion. Deferasirox has low affinity for zinc and copper, and does not cause constant low serum levels of these metals.

Deferasirox was first approved for the treatment of chronic iron overload due to blood transfusions (transfusional hemosiderosis) in adults and pediatric patients aged 2 years and older in the United States in November 2005 and is currently approved for this indication in more than 100 countries, including the European Union, Switzerland and Japan. Deferasirox has also been approved in more than 60 countries for the treatment of chronic iron overload in patients with non-transfusion dependent thalassemia aged 10 years and older.

### 11.2 Deferasirox Preparation and Administration

Deferasirox is for oral use and will be administered per manufacturers labeling for iron chelation..

## 12.0 ASSESSMENT OF EFFICACY AND TOXICITY

### 12.1 Efficacy Parameters

The primary endpoint is the proportion of patients that achieve erythroid hematologic improvement as defined by the modified IWG response criteria(39) at 6 months. Please see **Appendix G** for a table defining the response criteria for this study.

### 12.2 Method and Timing

All patients will be screened for eligibility following consent. Screening must be completed within 30 days of start of therapy. If the time period between screening assessments and start of therapy is greater than 30 days then screening tests must be repeated. The most recent screening labs prior to start of therapy will be considered the

baseline assessment upon which response by the modified IWG criteria will be based. Screening assessments will consist of CBC with differential, ferritin, hepatic and renal function tests and a bone marrow aspirate or biopsy. Women of child bearing potential must have a urine or serum pregnancy test performed within 7 days of start of deferasirox.

Follow up tests will consist of monthly CBC with differential, monthly ferritin levels, and monthly renal and hepatic function tests while the patient remains enrolled in the trial. Bone marrow aspiration or biopsy will be repeated at 3 months and 6 months following the start of deferasirox, and as clinically indicated. If at any point a patient is suspected to have disease progression, a bone marrow biopsy or aspirate may be obtained to document this progression. Physical exams and detailed history will be obtained on a monthly basis to screen for potential toxicities. The primary endpoint of hematologic improvement in the erythroid lineage will be assessed at 6 months following start of deferasirox. The secondary endpoints of hematologic improvement in granulocytes and platelets will also be assessed at 6 months. At the end of 6 months patients who do not respond will be offered the option of alternative treatment options including enrollment into clinical trials if possible.

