### 7.3 Duration of Therapy

#### 1. Screening phase (up to 4 weeks: Day -29 to Day -1)

Screening evaluations will be performed at one or more clinic visits to determine eligibility for the study.

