#### Laboratory Assessments

- CBC with differential
- Creatinine and GFR estimation
- Hepatitis Panel

Screening evaluations include laboratory evaluations as well as a bone marrow aspirate or biopsy. CBC with differential and record of transfusional requirements in the preceding 3 months will be obtained during the baseline screening. Testing for hepatotropic viruses will be performed during the screening phase to include: Hep A antibody, Hep B surface antibody, Hep B surface antigen, Hep B core antibody, Hep C antibody, and Hep C PCR. Baseline ophthalmologic and audiometric examinations will be performed during the screening phase. It is recommended that the screening bone marrow aspirate or biopsy be performed once a patient has been found to be otherwise eligible. The results from the screening bone marrow aspirate or biopsy will be used as the baseline for analyses. Baseline will be defined as the last assessment or procedure conducted prior to the initiation of deferasirox (Day 1). Baseline evaluations must be performed within 30 days of start of deferasirox except the baseline bone marrow biopsy which can have occurred within 30 days of the start of deferasirox and for pregnancy testing in women of childbearing potential which must be performed within 7 days of the start of deferasirox.

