**APPENDIX G**

**Modified IWG Response Criteria**

**Modified IWG Response Criteria for Hematologic Improvement**

Hematologic Improvement*	Response criteria (responses must last at least 8 wk)†
Erythroid response (pretreatment, < 11 g/dL)	Hgb increase by $\geq 1.5$ g/dL Relevant reduction of units of RBC transfusions by an absolute number of at least 4 RBC transfusions/8 wk compared with the pretreatment transfusion number in the previous 8 wk. Only RBC transfusions given for a Hgb of $\leq 9.0$ g/dL pretreatment will count in the RBC transfusion response evaluation
Platelet response (pretreatment, < $100 \times 10^9$ /L)	Absolute increase of $\geq 30 \times 10^9$ /L for patients starting with $> 20 \times 10^9$ /L platelets Increase from $< 20 \times 10^9$ /L to $> 20 \times 10^9$ /L and by at least 100%†
Neutrophil response (pretreatment, < $1.0 \times 10^9$ /L)	At least 100% increase and an absolute increase $> 0.5 \times 10^9$ /L†
Progression or relapse after HI‡	At least 1 of the following: At least 50% decrement from maximum response levels in granulocytes or platelets Reduction in Hgb by $\geq 1.5$ g/dL Transfusion dependence

Deletions to the IWG response criteria are not shown.

To convert hemoglobin levels from grams per deciliter to grams per liter, multiply grams per deciliter by 10.

Hgb indicates hemoglobin; RBC: red blood cell; HI: hematologic improvement.

\*Pretreatment counts averages of at least 2 measurements (not influenced by transfusions)  $\geq 1$  week apart (modification).

†Modification to IWG response criteria.

[figure not shown]
‡In the absence of another explanation, such as acute infection, repeated courses of chemotherapy (modification), gastrointestinal bleeding, hemolysis, and so forth. It is recommended that the 2 kinds of erythroid and platelet responses be reported overall as well as by the individual response pattern.

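### Section 12.2 bases modified IWG response on the latest screening labs and is not reconciled with Appendix G's average of at least two transfusion-free pretreatment values

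*Combined protocol and SAP*

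**What the plan says.** Section 12.1 sends the reader to Appendix G "for a table defining the response criteria for this study". The footnote to Appendix G reads "Pretreatment counts averages of at least 2 measurements (not influenced by transfusions", and adds that the measurements be at least 1 week apart. The hemoglobin route of erythroid response is a rise of at least 1.5 g/dL, lasting at least 8 weeks.

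Section 12.2 gives a different baseline. There, the latest screening results before treatment serve as the "baseline assessment upon which response by the modified IWG criteria will be based". It mentions neither averaging nor transfusion. The sentence before it is the repeat rule: "If the time period between screening assessments and start of therapy is greater than 30 days then screening tests must be repeated".

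Section 7.3 has a general rule: "Baseline will be defined as the last assessment or procedure conducted prior to the initiation of deferasirox (Day 1". It is also a last-value rule, but it does not name IWG response.

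The schedule does not settle the matter:
- Section 7.3 heads the screening period "Screening phase (up to 4 weeks: Day -29 to Day -1".
- Table 2 asks for a CBC within 7 days before treatment.
- The Appendix F calendar has a CBC, and a modified IWG assessment, at Screening and at Cycle 1 Day 1, the latter under Treatment Phase. It gives no minimum gap and no rule for combining the two.
- Transfusions are recorded (Section 7.3 and Appendix F), but nothing says how that record decides which CBC may serve as baseline.

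The other erythroid route is a reduction by an "absolute number of at least 4 RBC transfusions/8 wk compared with the pretreatment transfusion number in the previous 8 wk". It has its own baseline and is not affected.

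**The concern.** Two places define the pretreatment value from which the same rise is measured, and no text says which prevails. An analyst who follows Section 12.2 literally would use one value per patient, possibly one taken soon after a transfusion. An analyst who follows Appendix G would use a mean of at least two transfusion-free values. The two can class the same patient differently, and under Section 15.0 the test turns on whether 4 or more of 25 patients respond. The trial is open-label and single-arm, so a choice between the rules left until analysis could be made with the results in view.

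**Working it through.** **Design figures.** For X ~ Bin(25, p), P(X ≥ 4) is 0.0341 at p = 0.05 and 0.9038 at p = 0.25. Section 15.0 states 0.0336 and 0.9008. The small difference has no bearing here, because the baseline rule changes who counts as a responder and leaves the binomial cut-off alone.

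**The rules can disagree in both directions.** Take untransfused pretreatment values and an on-treatment value held for at least 8 weeks.
- 9.4 then 8.6, on treatment 10.2. Last value: 10.2 − 8.6 = 1.6, responder. Average: 10.2 − 9.0 = 1.2, non-responder.
- 8.6 then 9.4, on treatment 10.5. Last value: 10.5 − 9.4 = 1.1, non-responder. Average: 10.5 − 9.0 = 1.5, responder.

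**Why the rates differ.** With independent errors of SD s, the change from baseline to one later value has SD s√2 with a single baseline and s√1.5 with a mean of two. At s = 0.7 these are 0.99 and 0.86. With no true change, the chance that one later value is at least 1.5 above baseline is 6.5% against 4.0%.

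**Simulation of the full criterion.** The documents give no within-patient SD or autocorrelation, so all of the following are assumptions:
- true mean 9.2 g/dL and between-patient SD 0.9, with entry requiring a screening value of 10.0 or less (the cut is the protocol's);
- values at screening, Day 1 and months 1 to 6, with errors independent or autocorrelated at 0.5 per visit;
- response means three consecutive monthly values at least 1.5 g/dL above baseline.

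False responses with no drug effect (screening value / Day 1 value / mean of two):

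| SD | Independent | Autocorrelation 0.5 |
|---|---|---|
| 0.5 | 0.30 / 0.22 / 0.02% | 0.6 / 0.4 / 0.2% |
| 0.7 | 2.4 / 1.8 / 0.5% | 3.8 / 3.0 / 2.2% |
| 1.0 | 8.4 / 6.1 / 3.4% | 12.0 / 9.5 / 8.4% |

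For the trial, assume all 25 patients are on the hemoglobin route, 25% with a true rise of 2.0 g/dL and 75% with none. Expected patients of 25, at SD 0.5 / 0.7 / 1.0:

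| Quantity | Independent | Autocorrelation 0.5 |
|---|---|---|
| Classed differently, Day 1 vs mean of two | 1.1 / 1.5 / 2.2 | 0.7 / 1.1 / 1.9 |
| Net change, screening value minus mean of two | −0.1 / +0.4 / +1.1 | 0.0 / +0.3 / +0.7 |

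For Day 1 against the mean of two, the net change is at most about 0.5 patients. At SD 0.7 with independent errors it is 25 × (17.4% − 18.6%) = −0.3. The screening value shifts upward at the larger SDs because it also had to meet the entry cut, so it tends to be low by chance.

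At SD 0.7, P(at least 4 of 25) in this mixture is 0.77 / 0.65 / 0.71 with independent errors and 0.84 / 0.79 / 0.80 with autocorrelation (screening / Day 1 / mean of two).

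**Noise alone reaching 4 of 25, Day 1 vs mean of two.** At SD 0.7 it is 0.001 vs less than 0.0001 (independent) and 0.006 vs 0.002 (autocorrelated). At SD 1.0 it is 0.064 vs 0.010 and 0.21 vs 0.16. In that last case both rules far exceed the design error, so the baseline rule is not the main driver.

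**The case against.** The strongest reply is that the sections can be read together. The sentence in Section 12.2 directly follows the 30-day repeat rule, so it may only say which screening round counts. It never says a single value, and it does not exclude averaging. Section 12.1 stands just before it and names Appendix G, the more specific text. The calendar's two IWG assessments before or at the start of treatment fit a two-value baseline. All of that is fair, and it means the text does not show that the trial will use one value. What remains is that Section 12.2 expressly ties its baseline to IWG response and carries none of Appendix G's conditions.

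A reader might also infer that a last-value baseline inflates the type I error and favors a positive result. The documents do not support that. Nothing says which baseline rule the 5% null rate presumes. Disagreements run in both directions and partly cancel, and under the mixture above a Day 1 baseline gives slightly fewer responders than the average at SD 0.7. Only the screening-value reading shows a net upward shift, and not at SD 0.5.

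The opposite inference, that the effect is bounded and negligible, also fails. The 0.5-patient limit applies only to the Day 1 reading.

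**Conclusion.** The point holds as an unreconciled ambiguity in the primary endpoint's baseline, and as a direct conflict if Section 12.2 is read literally. It reaches the hemoglobin-rise route and the platelet and neutrophil endpoints. The effect is minor to moderate: about 0.7 to 2.2 of 25 patients are classed differently, with a net change in responders of at most about 0.5 (Day 1) or about −0.1 to +1.1 (screening value).

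These sizes rest on the assumed SDs, autocorrelation, true rise and responder share. Putting all 25 patients on the hemoglobin route pushes them up, since the real share is not given. Transfusion influence on the baseline was not simulated, so they are not an upper bound. Noise alone rarely reaches 4 of 25 at SD 0.7 or below, but that reassurance does not extend to SD 1.0 with autocorrelation. It should be fixed because it concerns the primary endpoint and the remedy is cheap.

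**What to change.** Amend Section 12.2 to say that, for the IWG response endpoints, baseline hemoglobin, platelets and ANC follow Appendix G: the mean of at least two pre-dose values, at least 1 week apart and not influenced by transfusion. Use the Screening CBC and a pre-dose Cycle 1 Day 1 CBC, both already in the calendar, or another pre-dose CBC within a stated window that is reconciled with the 30-day rule in Sections 7.3 and 12.2. State in Section 7.3 that its last-assessment rule does not apply to IWG response.

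Keep every patient in the denominator, in line with the intent-to-treat statement in Section 7.7. Prespecify one fallback for patients without two qualifying values, for example the one available untransfused value or, failing that, the last pre-dose value, flagged in the report. A sensitivity count using the last single value for everyone is optional.

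The cost is at least 1 week between the two CBCs, and now and then a repeat CBC or use of the fallback when the screening CBC falls too close to Day 1 or is affected by transfusion. Patients on a one-value fallback keep its extra noise (at SD 0.7, 1.8% rather than 0.5% false responses with independent errors). The observed response rate may shift slightly in either direction. The sample size and the 4-of-25 rule do not change.

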### **12.3 Other Parameters**

The secondary endpoints change in RBC transfusion requirements, change in serum ferritin, and safety and tolerability will be assessed in a continuous fashion during the entire duration of the study. Patients will remain on study for a maximum of one year. Patients will be assessed for AE and SAEs while they remain enrolled into the study. Patients will have an end of study visit day 30 following completion or withdrawal from the study.

## **13.0 DATA MANAGEMENT/CONFIDENTIALITY**

Study data will be recorded in a password-protected research database. Case report forms are generated from the database for review by the PI and study monitors. Clinical Statistics maintains a subject database at FHCRC to allow storage and retrieval of subject data collected from a wide variety of sources. The investigator will ensure that data collected conform to all established guidelines for coding, collection, key entry and verification. Each subject is assigned a unique patient number to assure subject confidentiality. Subjects will not be referred to by this number, by name, or by any other individual identifier in any publication or external presentation. The licensed medical records department, affiliated with the institution where the subject receives medical care, maintains all original inpatient and outpatient chart documents. Subject research files are scanned and stored in a secure database (OWL). OWL records are maintained by the FHCRC data abstraction staff. Access is restricted to personnel authorized by the Division of Clinical Research.

**14.0 ETHNIC and GENDER DISTRIBUTION: TARGETED ENROLLMENT****Projected Target Accrual  
ETHNIC AND GENDER DISTRIBUTION CHART**

TARGETED / PLANNED ENROLLMENT: Number of Subjects			
Ethnic Category	Gender		
	Females	Males	Total
Hispanic or Latino	1	1	2
Not Hispanic or Latino	9	14	23
Ethnic Category Total of All Subjects*	10	15	25
Racial Categories			
American Indian / Alaska Native	0	0	0
Asian	1	1	2
Native Hawaiian or Other Pacific Islander	0	0	0
Black or African American	0	0	0
White	9	14	23
Racial Categories: Total of All Subjects*	10	15	25

\*The "Ethnic Category Total of All Subjects" must be equal to the "Racial Categories Total of All Subjects". The projected accrual is based on demographic trends of the referral population and not on any perceived advantage or disadvantage of the intervention based on race, gender or ethnicity.

**15.0 STATISTICAL CONSIDERATIONS**

We estimate the rate of hematologic response to iron chelation with deferasirox to be 0.25 based on previously published studies in patients with MDS and iron overload. The null hypothesis that the true response rate is 0.05 will be tested against a one-sided alternative. The accrual goal is for a total of 25 patients. The null hypothesis will be rejected if 4 or more responses are observed in 25 patients. This design yields a type I error rate of 0.0336 and power of 0.9008 when the true response rate is 0.25. Descriptive statistics will be performed and the planned number of patients is estimated based on the patients we have that would meet eligibility criteria.

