### 4.2 Endpoints

#### 4.2.1 Primary Endpoint

The primary endpoint is the proportion of patients that achieve erythroid hematologic improvement as defined by the modified IWG response criteria at 6 months(39).

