**16.0 TERMINATION OF THE STUDY**

The PI may terminate the study at any time. The IRB and FDA also have the authority to terminate the study should it be deemed necessary. There is no planned interim analysis of this study and there are no early stopping rules in place for excessive toxicity. The study will be monitored by a designated DSMB which will meet every 6 months to review the protocol accrual and results including toxicity. The DSMB has the independent authority to terminate the study at their discretion. This information will be included in the consent form.

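### The stated type I error (0.0336) and power (0.9008) are not those of the single-stage 4-of-25 rule, which are 0.0341 and 0.9038; the stated pair probably comes from a two-stage design

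*Combined protocol and SAP*

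**What the plan says.** Section 15.0 (Statistical Considerations) gives every element of a single-arm, single-stage binomial test.

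- Null: "The null hypothesis that the true response rate is 0.05 will be tested against a one-sided alternative".
- Alternative: "We estimate the rate of hematologic response to iron chelation with deferasirox to be 0.25".
- Decision rule: "The null hypothesis will be rejected if 4 or more responses are observed in 25 patients".
- Claimed performance: "This design yields a type I error rate of 0.0336 and power of 0.9008 when the true response rate is 0.25".

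The section mentions no first stage and no futility bound. Section 16.0 (Termination of the Study) agrees with this: "There is no planned interim analysis of this study". Section 4.2.1 defines the primary endpoint as erythroid improvement "as defined by the modified IWG response criteria at 6 months". Section 10.0 provides for a semi-annual DSMB review: "Enrollment, response and toxicity data will be reviewed". Neither Section 10.0 nor Section 16.0 gives the DSMB a numerical response threshold.

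**The concern.** The rule in Section 15.0 is complete, so its type I error and power can be computed exactly. The results differ from the stated figures at the four-decimal precision the protocol uses. These are the only operating characteristics in the protocol, and they do not belong to the design as written.

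The difference could have two sources. The design may be single-stage, as the text says, with figures carried over from something else. Or a first stage may have been intended and its description lost. The two designs would be run differently: the two-stage rule that reproduces the figures would stop the trial after 15 patients with probability 0.95^15 = 0.463 if the null were true. The figures alone do not tell a reader which was meant.

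**Working it through.** **Inputs**, all from Section 15.0: n = 25; reject if X ≥ 4; p0 = 0.05; p1 = 0.25; one-sided. Stated results: 0.0336 and 0.9008.

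**1. Exact values for the rule as written.** With X ~ Bin(25, p), P(X ≥ 4) = 1 − [P(0) + P(1) + P(2) + P(3)].

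- At p = 0.05: 1 − (0.277390 + 0.364986 + 0.230518 + 0.093016) = **0.03409**.
- At p = 0.25: 1 − (0.000753 + 0.006271 + 0.025085 + 0.064106) = **0.90379**, carrying full precision.

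To four decimals these are 0.0341 and 0.9038. The plan's figures are not reproduced. The differences are 0.0341 − 0.0336 = 0.0005 and 0.9038 − 0.9008 = 0.0030.

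**2. Could an approximation explain it?** For 4 of 25:

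| Method | Type I error | Power |
|---|---|---|
| Stated | 0.0336 | 0.9008 |
| Exact binomial | 0.0341 | 0.9038 |
| Poisson | 0.0383 | 0.8697 |
| Normal, continuity correction | 0.0195 | 0.8980 |
| Normal, no correction | 0.0058 | 0.8507 |

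None gives the stated pair.

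**3. Could it be another single-stage rule?** Among all rules with n from 5 to 100 and any cutoff, none gives both figures. Only 8 of 75 gives 0.0336, and its power is 0.9995. Only 18 of 91 gives 0.9008, and its type I error is below 0.0001.

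**4. Two-stage rules with a futility stop.** Stop if at most r1 of the first n1 patients respond; otherwise continue to n and reject at r or more in total:

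P(reject) = Σ over x1 from r1 + 1 to n1 of Bin(x1; n1, p) × P(X2 ≥ r − x1), with X2 ~ Bin(n − n1, p).

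For n1 = 15, r1 = 0, n = 25, r = 4, the contributions are:

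| x1 | p = 0.05 | p = 0.25 |
|---|---|---|
| 1 | 0.365756 × 0.011504 = 0.004207 | 0.066817 × 0.474407 = 0.031699 |
| 2 | 0.134752 × 0.086138 = 0.011607 | 0.155907 × 0.755975 = 0.117862 |
| 3 | 0.030733 × 0.401263 = 0.012332 | 0.225199 × 0.943686 = 0.212517 |
| 4 or more | 0.005467 | 0.538713 |
| **Total** | **0.03361** | **0.90079** |

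Both totals round to the stated figures. Over total n from 10 to 44, cutoffs 1 to 9, and every n1 and r1 below the cutoff, this is the only design that matches both. Neighbouring first stages do not match: n1 = 14 gives 0.0333 and 0.8987, and n1 = 16 gives 0.0338 and 0.9021.

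**5. Cross-check.** The two designs should differ by exactly the chance of 0 responses in the first 15 followed by 4 or more in the next 10.

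- At p = 0.05: 0.95^15 × P(X ≥ 4 of 10) = 0.463291 × 0.001028 = 0.00048, and 0.03409 − 0.03361 = 0.00048.
- At p = 0.25: 0.75^15 × P(X ≥ 4 of 10) = 0.013363 × 0.224125 = 0.00300, and 0.90379 − 0.90079 = 0.00300.

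**6. Plausibility of the two-stage source.** The matching rule is also the Simon minimax design for these two rates with type I error at most 0.05 and power at least 0.90. Those limits are assumed here, since the protocol states no nominal level. Its expected sample size under the null is 15 + (1 − 0.4633) × 10 = 20.4.

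**The case against.** The strongest reply concerns weight, not arithmetic. The total of 25 and the cutoff of 4 do not change, and no nominal alpha is stated that could be breached. True type I error stays below a conventional 0.05, and true power is slightly better than claimed. No patient and no analysis is affected by changing the two numbers.

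The operative text is also consistently single-stage. Section 15.0 gives one total and one rule, Section 16.0 plans no interim analysis, and Section 14.0 targets 25 subjects. On that reading the document already says what the current design is, and only the origin of the numbers is unknown. A two-stage origin cannot be proved from the documents.

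Much of this stands. The effect is small, the origin is an inference, and the single-stage reading should be the default. The reply does not rescue the sentence, because the written design does not have the stated type I error or power. The match on both figures, with the same total, cutoff and response rates, is close enough to justify asking the sponsor whether a first stage was dropped.

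Two points on Section 10.0 do not change this. Its list of items for DSMC review includes stopping rules, but that wording may be generic and does not establish a lost first stage. The DSMB's semi-annual review gives oversight under either design, although a discretionary review is not the same as a numerical futility bound.

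**Conclusion.** The concern holds. For the rule in Section 15.0, type I error is 0.0341 (0.0005 above the stated value) and power at a 25% response rate is 0.9038 (0.0030 above). These are exact binomial results and assume only that each of the 25 patients counts once as responder or non-responder, independently and with the same response probability.

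That the stated pair comes from a two-stage design with a stop at 0 of 15 is probable but not established. The point should be corrected and the intended design confirmed. It does not affect the sample size or the 4-of-25 decision, and it is not a patient-safety gap.

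**What to change.** **Default.** Sections 15.0 and 16.0 both describe a single stage, so in the last part of the Section 15.0 design statement replace 0.0336 with 0.0341 and 0.9008 with 0.9038. This costs two numbers in one sentence, with no extra patients and no change to the decision rule. Ask the sponsor to confirm that no first stage was intended.

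**Only if the sponsor confirms a two-stage design.** Keep 0.0336 and 0.9008, and make these changes:

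- Section 15.0 states the first-stage look: its size, its stopping bound, and what happens to accrual until the 6-month endpoint is known for the first 15 patients.
- Section 16.0 is reconciled with that look, since it now says none is planned.

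The cost is then edits to both sections, 0.3 percentage points of power relative to the single stage (0.9038 − 0.9008), and either an accrual pause of up to about 6 months after the 15th patient or a stated rule for patients enrolled in the meantime.
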